7.6 Study Hypotheses

Hypothesis 1: Participants are hypothesized to rate the intervention as not burdensome, easy to access, and appealing. Additionally, recruitment and retention rates are predicted to be $\geq 75\%$.

Hypothesis 2: Participants in the treatment arm will (A) increase MVPA relative to those in the comparison arm at post-intervention, (B) decrease SB relative to those in the comparison arm, and (C) demonstrate an increase in VO_{2max} at post-intervention relative to those in the comparison arm.

7.7 Sample Size Considerations

A sample size of $n=50$ per group will provide 80% power to detect a large effect size⁵⁹ for the standardized mean difference, still allowing for possible detection of a medium effect size ($d=.6$) with 55% power. Effect sizes from relevant studies examining change in MVPA range from large ($d=.94$; CHD adolescents in a motivational interviewing-style exercise intervention)²⁸ to small ($d=.17$; older adults with cardiovascular risk factors).²² Thus, our primary goal is to estimate an initial effect size for our intervention in our population, with a secondary goal to detect large effect sizes that may exist for study outcomes. However, effect estimation with a relatively small sample size should be interpreted with caution, as it may under or overestimate the sample size.^{60,61}

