REDCap	Research Electronic Data Capture
VO _{2max}	Peak Oxygen Uptake

PROTOCOL SUMMARY

Title:	Congenital Heart Disease Physical Activity Lifestyle Study (CHD-PALS)
Abstract:	Over 40,000 infants are born in the U.S. with congenital heart disease (CHD) each year, and with advancements in medicine, more than 90% of these individuals now live well into adulthood. This growing, and aging, population of CHD survivors is at risk for developing cardiac-related complications such as coronary disease, heart failure, and hypertension, which fortunately are responsive to lifestyle change. An American Heart Association (AHA) Scientific Statement highlights the important health benefits gained from increasing physical activity (PA) among children and adults with CHD, noting research evidence of better vascular health, reductions in hypertension, and lower rates of obesity. Despite this, evidence suggests that CHD survivors are less active than healthy controls, placing them at an elevated risk for preventable morbidity and premature mortality. Therefore, the currently study adapts a PA lifestyle intervention to adolescent emerging adult CHD survivors (ages 15-25) who have moderate to complex CHD with the goal of increasing MVPA and decreasing SB. The study is split into 2 phases; a total of 125 adolescent and caregiver dyads and emerging adults will participate in Phase 1 to determine participants' eligibility for Phase 2. Phase 2 is the randomized control trial in which a total of 70 adolescents and 30 emerging adults are randomized to either the comparison arm (Fitbit and exercise prescription) or the intervention arm (Fitbit, exercise prescription, AND videoconferencing sessions with a coach).
Population:	Participants: For Phase 1 we aim to recruit 85 adolescents (ages 15 – 18 at enrollment) and 40 emerging adults (ages 18 – 25 at enrollment), who have moderate to complex CHD, along with caregivers for adolescents. For Phase 2 we aim to recruit 70 adolescent and caregiver dyads (35 per arm) and 30 emerging adults (15 per arm).
Study Duration:	4 years (2017-2021)
Participation Duration:	Phase 1: 2 weeks Phase 2: 22 weeks with a 6-month follow-up assessment

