3.2 Study Outcome Measures

3.2.1 Primary Outcome Measure

Number of minutes spent in MVPA as measured by an accelerometer.

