5 STUDY ENROLLMENT AND WITHDRAWAL

The total target sample size for enrollment in Phase 1 is 125 participants and in Phase 2, 100 participants (50 participants per arm). A higher enrollment is expected for Phase 1 than Phase 2 to account for some participants being deemed ineligible to proceed with Phase 2.

Potential participants are identified through upcoming cardiology clinic rosters who meet the age (15-25 years of age) and diagnosis (moderate to complex CHD³) criteria. Study personnel check the patient's medical record to verify eligibility. If a patient appears to be eligible, study staff confirm with the attending cardiologist that no additional reason/s preclude the adolescent from participating, including limitations to engaging in MVPA. Next, the patient, or if an adolescent, the patient's caregiver(s) (or their legal guardian of record), is sent a letter from the attending cardiologist, notifying them about the study and that study personnel will be in contact. An "opt out" phone number is provided so that the caregiver(s) can call and leave a message if they do not wish to be contacted. Approximately 1 week later, if no message was received, caregiver(s) are called by study personnel. During the phone conversation, the objectives and primary components of the study are discussed. If a patient and/or caregiver are interested, verbal consent/assent (if <18 years of age) is obtained for completing online questionnaires and the exercise stress test at NCH is scheduled. During the stress test visit, written consent/assent for the stress test and accelerometer assessment is obtained. If a patient and/or a caregiver cannot be reached via phone, they are approached during their clinic appointment in person.

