7.9 Analysis Plan

Aim 1: Evaluate the feasibility of the intervention.

The mean/median ratings by participants on multiple dimensions of the intervention will be computed. Recruitment rate will be calculated as a percentage of those recruited out of those approached. Percent adherence across sessions will be calculated for those in the intervention arm as the number of sessions attended out of 8. The retention rate will be identified by dividing the number of participants who do not complete the study by the number of participants enrolled.

Verbal responses collected during the focus groups will be transcribed and then coded so that the frequencies of suggestions can be calculated.

Aim 2: Examine preliminary efficacy of the intervention on time spent in MVPA.

First, independent sample t-tests (continuous variables) or chi-square tests (categorical variables) will compare study arms on all variables at baseline, *including biological considerations such as sex and disease status*, to determine if statistically significant differences are present. Only the pre-specified covariates of baseline minutes spent in MVPA and baseline VO_{2max} will be included in the primary analyses.⁶² However, if statistically significant differences are found at baseline, those variables will be examined as covariates in all statistical models of interest in an exploratory fashion.

Second, the following statistical model for repeated measures (RM), based on maximum likelihood estimation, will be employed,⁶³ $y_{it} = \beta_0 + \beta_1 Time_t + \beta_2 Time_t \times Trt_i + \varepsilon_{it}$, where implicitly it is assumed that there is no main effect of Trt_i , y_{it} is minutes in MVPA at time t , $Time_t$ is coded as 0 for baseline and 1 for post-intervention, and the primary effect of interest is β_2 , which is the difference between groups on participants' minutes in MVPA. In this RM model, baseline levels of minutes in MVPA is constrained to have equal means across groups by assuming there is no main effect of the intervention, Trt_i . This constraint yields a statistical test for β_2 analogous to the test of the treatment group main effect per ANCOVA without requiring list-wise deletion to account for missing data. A similar strategy will be taken for analyzing change in SB and VO_{2max} as secondary outcomes.

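### Section 7.7 gives 55% power at d=.6 with 50 per arm; under a two-sided 0.05 t-test it is 84%, and the 80% for a large effect is also too low

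*Combined protocol and SAP*

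**What the plan says.** Section 7.7 states "A sample size of $n=50$ per group will provide 80% power to detect a large effect size", on the scale of a standardized mean difference, "still allowing for possible detection of a medium effect size ($d=.6$) with 55% power". It puts no number on the large effect in that sentence. Later it says that effect sizes in related studies "range from large ($d=.94$; CHD adolescents in a motivational interviewing-style exercise intervention" down to a small d=.17. It makes estimation of an initial effect size the primary goal and detection of large effects a secondary one.

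The sample size is consistent elsewhere. Section 5 gives "in Phase 2, 100 participants (50 participants per arm", and the Protocol Summary gives "70 adolescent and caregiver dyads (35 per arm) and 30 emerging adults (15 per arm", which again makes 35 + 15 = 50 per arm.

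The single primary outcome (section 3.2.1) is "Number of minutes spent in MVPA as measured by an accelerometer". Section 7.9 analyses it with a two-timepoint model in which time "is coded as 0 for baseline and 1 for post-intervention" and baseline means are constrained equal. It describes the resulting test as "analogous to the test of the treatment group main effect per ANCOVA without requiring list-wise deletion". Section 7.6 predicts retention of at least 75%. Neither document gives an alpha level, a sidedness or a multiplicity adjustment.

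**The concern.** Section 7.7 puts sample size, effect size and power together, so the d=.6 figure can be checked directly once an alpha is assumed. A power near one half at d=.6 with 50 per arm is implausibly low for an ordinary two-group comparison. The two percentages also cannot both hold at the usual alpha, because 80% power is already reached below d=.6.

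This section is where the protocol says what the trial can detect. A reader who believes power at d=.6 is 55% would treat a null result there as little better than a coin toss, when the design would usually detect such an effect. The pilot is also meant to shape the next phase of research. The error is in the conservative direction, so no participant and no planned analysis is affected.

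**Working it through.** **Inputs.** n = 50 per arm (sections 5 and 7.7); d = .6 with stated power 55%, a large effect with stated power 80%, and d = .94 labelled large (section 7.7); SD = 1, because the effect is standardized; 75% as the retention floor (section 7.6). Assumed: two-sided alpha 0.05, a two-sample t-test, and d = 0.8 as a second value for large.

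**Formula.** Power = P(T > c), where T is noncentral t with 2n − 2 degrees of freedom and noncentrality d√(n/2), and c is the 97.5th percentile of central t. The opposite tail is negligible here.

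**The plan's figures at n = 50.** There are 98 degrees of freedom, c = 1.984 and √(50/2) = 5.

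| d | Noncentrality | Power | Stated |
|---|---|---|---|
| .6 | 3.0 | 84.4% | 55% |
| 0.8 (assumed large) | 4.0 | 97.7% | 80% |
| .94 | 4.7 | 99.65% | 80% |

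Solving for d gives 80% power at d = 0.566 and 55% power at d = 0.421. Neither stated figure is reproduced.

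**Could the unstated alpha explain it?** One-sided 0.05 moves further away: 90.9% at d = .6 and 99.0% at d = 0.8. Forcing 55% at d = .6 needs a two-sided alpha of about 0.005, and power is then about 87% at d = 0.8 and 96% at d = .94. No single alpha gives 55% at d = .6 together with 80% at either value for large.

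**Could attrition explain it?** 75% of 50 is 37.5, so 37 or 38 per arm.

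| n per arm | d = .6 | d = 0.8 | d for 80% power |
|---|---|---|---|
| 37 | 72.1% | 92.4% | 0.660 |
| 38 | 73.3% | 93.1% | 0.651 |

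The stated 55% is still 17–18 points low. Power of 80% at d = .6 needs 44.6, so 45 per arm with outcomes (90% of 50).

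The likelihood model does not recover this loss. With two timepoints and equal baseline means, participants with a baseline only leave the variance of β₂ unchanged. For 37 completers per arm that variance (SD = 1) is 2(1 − ρ²)/37, where ρ is the baseline-to-post correlation. This gives 0.05405, 0.04919, 0.04054 and 0.02757 at assumed ρ of 0, 0.3, 0.5 and 0.7, with or without 13 further baseline-only participants per arm.

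**Could the planned model explain it?** No. A test equivalent to ANCOVA has about the t-test's power at ρ = 0 (84.4% at d = .6) and more as ρ rises (92.9% at ρ = 0.5).

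**Assumptions that come close to 80% and 55%.**

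| Assumption | d = 0.8 | d = .6 |
|---|---|---|
| 25 per arm | 79% | 54.7% |
| Change score, ρ = 0, 50 per arm | 80.0% | 55.6% |
| Alpha 0.05/3, 37–38 per arm | 84–85% | 55–57% |
| Change score, ρ = 0.25, 37–38 per arm | 79–80% | 55–56% |

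The change-score rows divide d by √(2(1 − ρ)). At ρ = 0 this is the same as halving n. At ρ = 0.25 with 37.5 per arm the effective n is 37.5/(2 × 0.75) = 25. Solving directly, 55% at d = .6 needs 25.2 per arm and 80% at d = 0.8 needs 25.5. That suggests, but does not prove, a calculation for 50 participants in total.

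**The case against.** The strongest reply is that 84% is not established as the true power, because alpha, sidedness, test, evaluable n and the SD that standardizes d are all unstated. Section 7.7 speaks of studies of change in MVPA. A change-score test with 75% retention and a baseline-to-post correlation of 0.25 gives essentially the published pair, and it uses one of the protocol's own numbers. That arithmetic is right, and it means the origin of the figures cannot be settled. It does not rescue the text: neither the correlation nor the change-score test is stated, section 7.7 makes no attrition allowance, and section 7.9 plans an ANCOVA-type test.

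It is also fair that d=.94 is one published estimate at the top of a range and not a design value, and that 0.8 is an assumption. The conclusion needs neither, because 80% power falls at d=0.57, below the section's own medium effect.

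The 75% scenario treats predicted retention as the share with a usable post-intervention outcome, which the protocol does not say. It is a sensitivity check only. The calculations also leave out baseline VO2max, the second prespecified covariate in section 7.9.

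Finally, this is a preliminary-efficacy study with estimation as its primary goal, no interim analysis is planned, and the error is conservative. All of that stands and limits the importance of the point. It does not make the published percentages correct.

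**Conclusion.** The concern holds. At 50 per arm, with an assumed two-sided alpha of 0.05 and a two-sample t-test, power at d=.6 is 84% against the stated 55%. For a large effect it is 98% (d=0.8) to over 99% (d=.94) against the stated 80%. The d=.6 comparison is the firmer one, because n, d and power are all given; the 80% figure fails for any effect above d=0.57. No assumption stated in the documents yields the published pair, and that about 25 per arm does so is an inference. The figures should be corrected, but the trial is not underpowered for the effects it names.

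**What to change.** Rewrite the power statement in section 7.7 to give alpha, sidedness, test, the numeric value meant by a large effect, and the number per arm expected to supply outcomes. For example, under two-sided alpha 0.05 and a two-sample t-test:

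- 50 per arm gives 80% power for d=0.57, 84% for d=0.6 and 98% for d=0.8.
- With outcomes from 75% (37–38 per arm), power is 80% for d=0.65–0.66, 72–73% for d=0.6 and 92–93% for d=0.8.
- The baseline-constrained model in section 7.9 has at least about this power, rising with the baseline-to-post correlation.

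If a different sample size, a change score, an adjusted alpha or an attrition allowance produced the published figures, state it and reconcile it with section 7.9. The cost is one paragraph of protocol wording. Enrolment, the analysis and the stated goals need not change.

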7.8 Planned Interim Analyses (if applicable)

No interim analysis is planned.

7.9 Analysis Plan

Aim 1: Evaluate the feasibility of the intervention.

The mean/median ratings by participants on multiple dimensions of the intervention will be computed. Recruitment rate will be calculated as a percentage of those recruited out of those approached. Percent adherence across sessions will be calculated for those in the intervention arm as the number of sessions attended out of 8. The retention rate will be identified by dividing the number of participants who do not complete the study by the number of participants enrolled.

Verbal responses collected during the focus groups will be transcribed and then coded so that the frequencies of suggestions can be calculated.

Aim 2: Examine preliminary efficacy of the intervention on time spent in MVPA.

First, independent sample t-tests (continuous variables) or chi-square tests (categorical variables) will compare study arms on all variables at baseline, *including biological considerations such as sex and disease status*, to determine if statistically significant differences are present. Only the pre-specified covariates of baseline minutes spent in MVPA and baseline VO_{2max} will be included in the primary analyses.⁶² However, if statistically significant differences are found at baseline, those variables will be examined as covariates in all statistical models of interest in an exploratory fashion.

Second, the following statistical model for repeated measures (RM), based on maximum likelihood estimation, will be employed,⁶³ $y_{it} = \beta_0 + \beta_1 Time_t + \beta_2 Time_t \times Trt_i + \varepsilon_{it}$, where implicitly it is assumed that there is no main effect of Trt_i , y_{it} is minutes in MVPA at time t , $Time_t$ is coded as 0 for baseline and 1 for post-intervention, and the primary effect of interest is β_2 , which is the difference between groups on participants' minutes in MVPA. In this RM model, baseline levels of minutes in MVPA is constrained to have equal means across groups by assuming there is no main effect of the intervention, Trt_i . This constraint yields a statistical test for β_2 analogous to the test of the treatment group main effect per ANCOVA without requiring list-wise deletion to account for missing data. A similar strategy will be taken for analyzing change in SB and VO_{2max} as secondary outcomes.

Aim 3: Explore mechanisms of change in MVPA and SB, as specified by the Theory of Planned Behavior, including attitudes (i.e., knowledge about and belief in positive outcomes from PA), normative beliefs (i.e., participant-report of family/friend/physician beliefs about and support of PA) and perceived behavioral control (i.e., barriers and efficacy for PA).

Differences between intervention and comparison arm participants on attitudes, normative beliefs and perceived control at the interim assessment will be examined using independent sample t-tests. These variables then will be included in longitudinal mediation models exploring the indirect effects of the intervention on change in behavior as compared to the comparison group on MVPA and SB via the identified mechanisms at the interim assessment. We will use Mplus, which employs bootstrapping to statistically test mediators of the pathway of interest, both individually and simultaneously, to estimate whether one accounts for more variance in the

treatment effect relative to another. We will follow guidelines for testing longitudinal mediation within Cole & Maxwell⁶³ and MacKinnon.⁶⁴ We acknowledge that due to the limited sample size, significant mediation may not be detectable. However, indirect paths nearing significance will have important implications for the future refinement of the intervention by allowing us to focus on the most salient mechanisms of behavior change for the R01 application. Significant Pearson correlations between baseline levels of proposed mechanisms of change and MVPA and SB may also be informative for adjusting the intervention prior to the R01 application to more directly address these factors. Sex will be explored as a potential moderator of intervention effects.

Other Analyses: Relationships between other predictors and study outcomes will also be explored. For example, cardiac-related anxiety, body image disturbance, caregiver perceptions will be examined as possible predictors of participants' willingness to participate in Phase 2 of the study, as well as change in the study outcome variables using linear regression.

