3 OBJECTIVES

3.1 Study Objectives

A total of 125 CHD survivors (ages 15 - 25), and caregivers for adolescent participants, are anticipated to be enrolled in Phase 1 of the study, which establishes eligibility for Phase 2. For Phase 2, the randomized trial portion of the study, we plan to enroll a total of 70 adolescents and caregiver, and 30 emerging adults. The aims of the study are to:

1. *Aim 1: Assess feasibility of the intervention to participants based on subjective ratings.*
Hypothesis 1: Participants are hypothesized to rate the intervention as not burdensome, easy to access, and appealing. Additionally, recruitment and retention rates are predicted to be $\geq 75\%$.
2. *Aim 2: Evaluate preliminary efficacy of the intervention on time spent in MVPA and SB, as well as improvement in cardiorespiratory fitness as assessed by changes in VO_{2max} .*
Hypothesis 2: Participants in the intervention arm will (A) increase MVPA relative to those in the comparison arm at post-intervention, (B) decrease SB relative to those in the comparison arm, and (C) demonstrate an increase in VO_{2max} at post-intervention relative to those in the comparison arm.
3. *Aim 3 (Exploratory): Explore mechanisms of change in MVPA and SB, as specified by the Theory of Planned Behavior, including attitudes (i.e., knowledge about and belief in positive outcomes from PA), normative beliefs (i.e., participant-report of family/friend/physician beliefs about and support of PA) and perceived behavioral control (i.e., barriers and efficacy for PA).*

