5.3.3 Handling of Withdrawals

If withdraw occurs because a participant's cardiologist determines that the participant should no longer be in the study due to a change in medical status or the participant and/or caregiver request to be withdrawn, participants are asked to complete the assessments if possible and are included in intent-to-treat analyses.

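### The retention rate is defined as non-completers over enrolled, which is attrition, so the predicted 75% threshold would be read backwards

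*Combined protocol and SAP*

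**What the plan says.** Section 7.9, Aim 1, sets out how feasibility will be summarised. On retention it states: "The retention rate will be identified by dividing the number of participants who do not complete the study by the number of participants enrolled". The same paragraph defines two companion measures. For recruitment: "Recruitment rate will be calculated as a percentage of those recruited out of those approached". Session adherence in the intervention arm is taken "as the number of sessions attended out of 8".

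Hypothesis 1, in section 7.6, says that "recruitment and retention rates are predicted to be" at least 75%. The same prediction appears in the Protocol Summary, section 2.2 and section 3.1. Section 5 gives the enrolment targets: "The total target sample size for enrollment in Phase 1 is 125 participants and in Phase 2, 100 participants (50 participants per arm").

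**The concern.** The numerator counts the participants who were lost. A quantity labelled retention that rises as more people drop out contradicts its own name, and it contradicts a hypothesis in which a high value is the good result.

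Feasibility is Aim 1, and retention is one of only two feasibility measures with a numeric threshold. The stated rationale for the study is to obtain pilot data for the next phase of investigation. An analyst who follows the text would report the wrong quantity and, over the range of results the sponsor expects, the wrong verdict on the prediction. An analyst who quietly computes completers over enrolled would be departing from the written plan.

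**Working it through.** **Inputs**

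- Formula as written: non-completers / enrolled (section 7.9, Aim 1).
- Threshold: at least 75% (section 7.6, Hypothesis 1). It is a stated prediction and is not derived from other inputs, so there is no figure to reproduce.
- Enrolled, N: 100 for Phase 2 and 125 for Phase 1 (section 5).
- Completers, C: the document gives no expected dropout, so C is an assumption and is varied from 0 to N.

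**Formulas**

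- As written: (N − C) / N. It reaches 0.75 when C ≤ 0.25 N.
- Retention in the ordinary sense: C / N. It reaches 0.75 when C ≥ 0.75 N.

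The two quantities add up to 1, so both cannot be 0.75 or more.

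**Results at N = 100**

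| Completers C | As written, (100 − C)/100 | At least 75%? | Completers/enrolled, C/100 | At least 75%? |
|---|---|---|---|---|
| 90 | 10% | no | 90% | yes |
| 80 | 20% | no | 80% | yes |
| 75 | 25% | no | 75% | yes |
| 50 | 50% | no | 50% | no |
| 25 | 75% | yes | 25% | no |
| 10 | 90% | yes | 10% | no |

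The verdicts are opposite for C of 75 or more and for C of 25 or fewer. For C from 26 to 74 both definitions miss the threshold. At N = 125 the pattern is the same, and both miss for C from 32 to 93.

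**Direction of the companion measures.** Recruitment is recruited over approached, and adherence is sessions attended over 8. Both put the favourable count on top. Retention alone is inverted.

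**Two gaps in the same sentence**

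- *Denominator.* Enrolment is used for both phases. With 80 completers, 80/100 = 80% but 80/125 = 64%, on opposite sides of 75%.
- *Completion.* It could mean the post-intervention assessment (section 6.5) or the 6-month follow-up (section 6.7). Section 5.3.3 adds a further case. After a withdrawal on a cardiologist's decision or at the participant's or caregiver's request, "participants are asked to complete the assessments if possible and are included in intent-to-treat analyses". Someone who leaves the intervention but is still assessed could therefore be counted either way.

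**Precision.** For 80 of 100, the exact binomial 95% confidence interval is 0.708 to 0.873, or 71% to 87%. Even an observed 80% would not exclude true retention below 75%.

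**The case against.** The best defence is that this is a slip of wording, with two words too many, and that the intent is plain from the hypothesis and from the neighbouring measures. A competent analyst would be unlikely to report 80% completion as failed feasibility, and the raw counts would expose a mislabelled figure. Retention does not enter the primary outcome or the Aim 2 model. The 75% is a prediction, and no progression or stopping decision depends on it: sections 5.3.4, 7.4 and 10.5 rest termination or halting on safety findings and on DSMB or IRB judgement. The conclusion also does not reverse for every result, and a full redefinition does more than the minimal repair.

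Much of this stands as a matter of scope. The threshold should be called a prediction. The reversal is confined to completion of at least 75% or at most 25%. The choice of visit and denominator belongs to the study team. None of it rescues the sentence, because the intended direction has to be inferred against the explicit text and the range where the verdict reverses includes every outcome that Hypothesis 1 predicts.

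**Conclusion.** The concern holds: the definition is wrong as written. Section 7.9 defines attrition, labels it retention, and contradicts Hypothesis 1. At 100 enrolled, the 75% prediction would be met only with 25 or fewer completers, and missed by every result of 75 or more.

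The direction of the error needs no assumption beyond the text. The completer counts used to show its size are illustrative, and the size at N = 100 assumes that enrolled refers to Phase 2. The effect is limited to the Aim 1 retention result; the primary efficacy analysis is untouched. It should be corrected before the feasibility results are reported.

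**What to change.** Replace the sentence in section 7.9, Aim 1. The minimum is to put completers in the numerator. The new sentence should also state which assessment defines completion and which phase supplies the denominator.

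A workable definition is the number of randomised Phase 2 participants who complete the post-intervention assessment, divided by the number randomised. Report it overall and by arm, compare it with 75%, and give an exact 95% confidence interval. If the team prefers the 6-month follow-up as the completion point, that is acceptable provided it is written down. The sentence should also say that a participant who stops the intervention but provides the assessment counts as retained, or that they do not.

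The cost is a one-sentence amendment to the analysis plan. It needs no new data and no change to the sample size or to study procedures.

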Estimated Time to Complete Enrollment (n=125):	3 years

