6.3 Phase 2: Enrollment in the RCT

Eligible participants from Phase 1 are met at their home (or the hospital if preferred) to receive their Fitbit and exercise prescription, which is based on the results of their stress test. After receiving the Fitbit and exercise prescription, the participant's arm designation is revealed by opening an envelope that has been prepared by the study statistician, [name]. Prior to opening the envelop, the study PI, study staff, and the participant are blind to the study arm designation.

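### The retention formula gives attrition as written and names no arm; even with the numerator corrected, one overall rate cannot show whether the coached arm is retained

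*Combined protocol and SAP*

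**What the plan says.** Section 7.9 heads this part "Aim 1: Evaluate the feasibility of the intervention". Session adherence is restricted by arm: "Percent adherence across sessions will be calculated for those in the intervention arm as the number of sessions attended out of 8". The next sentence obtains retention by "dividing the number of participants who do not complete the study by the number of participants enrolled". The denominator, "by the number of participants enrolled", names no arm and no phase, and the sentence names no visit that marks completion.

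Section 7.6 states the expectation: "recruitment and retention rates are predicted to be" at least 75%. The Protocol Summary and Sections 2.2 and 3.1 repeat it. None of them names an arm, and none makes it a condition for going on to the next study.

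Enrolment is used for both phases. Section 5 says: "The total target sample size for enrollment in Phase 1 is 125 participants and in Phase 2, 100 participants (50 participants per arm"). The Protocol Summary has "Estimated Time to Complete Enrollment (n=125"), which is the Phase 1 figure. Section 6.3 is headed "Phase 2: Enrollment in the RCT".

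Two assessments could mark completion: post-intervention at weeks 20–26 (Section 6.5) or the 6-month follow-up at weeks 46–50 (Section 6.7).

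**The concern.** There are two faults in one sentence.

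The first is definite. A count of non-completers over a count enrolled is a loss rate, and it cannot sensibly be set against a prediction of at least 75% retained.

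The second remains once the numerator is put right. The coaching is what is being tested for feasibility: eight videoconference sessions over 20 weeks, text messages between sessions, and a request to sync the Fitbit daily (Sections 5.4 and 5.7). The comparison arm has none of this, and after the initial instruction it is not contacted again about the Fitbit. Its retention is informative about running a trial but not about whether people stay with coaching, yet it supplies half of the denominator. Because adherence is limited to the intervention arm one sentence earlier and retention is not, a single overall rate is the natural reading.

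The study is meant to supply pilot data for a later efficacy study. An overall figure near 75% could be carried forward as evidence that the coached programme holds its participants when the coached arm did not. Loss that differs by arm also bears on Aim 2, and the plan asks for no by-arm account of it.

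**Working it through.** The figure of 75% is a prediction without a derivation, so there is no calculation in the plan to reproduce. The inputs from the documents are 50 per arm and 100 in Phase 2, 125 in Phase 1 (Section 5), and the 75% prediction (Section 7.6). The documents give no dropout rate, so all arm-specific rates below are assumptions.

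**1. The formula as written.** Rate = non-completers / enrolled. With 10 losses among 100, 10/100 = 10%. A value of 75% or more would require at least 75 non-completers.

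**2. Numerator corrected, arms combined.** Overall rate = (intervention completers + comparison completers) / 100. To reach 75%, the intervention arm needs at least 75 minus the comparison completers:

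| Comparison completers | Fewest intervention completers for 75/100 |
|---|---|
| 40/50 (80%) | 35/50 (70%) |
| 45/50 (90%) | 30/50 (60%) |
| 50/50 (100%) | 25/50 (50%) |

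Judged alone, the intervention arm needs 38/50, since 0.75 × 50 = 37.5.

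**3. How often the two disagree.** Let A ~ Bin(50, p_int) and B ~ Bin(50, p_comp), independent. The discordance is P(A + B ≥ 75 and A ≤ 37), computed exactly:

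| True rates, intervention / comparison | P(overall ≥ 75%) | P(intervention ≥ 75%) | Discordance |
|---|---|---|---|
| 65% / 95% | 0.93 | 0.07 | 0.86 |
| 65% / 90% | 0.78 | 0.07 | 0.71 |
| 70% / 90% | 0.92 | 0.22 | 0.70 |
| 70% / 85% | 0.77 | 0.22 | 0.55 |
| 60% / 90% | 0.56 | 0.01 | 0.54 |
| 80% / 90% | >0.99 | 0.81 | 0.18 |
| 75% / 75% | 0.55 | 0.51 | 0.15 |
| 80% / 80% | 0.91 | 0.81 | 0.13 |
| 65% / 75% | 0.16 | 0.07 | 0.11 |
| 85% / 85% | >0.99 | 0.97 | 0.03 |

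Discordance is common when the coached arm is truly below 75% and the average of the two arms is at or above it. Elsewhere it is modest or small.

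**4. Enrolled read as Phase 1.** If those who never enter Phase 2 count as not retained, the most that can be reached is 100/125 = 80%. Reaching 75% needs 94 completers, since 0.75 × 125 = 93.75. At most 50 can come from the comparison arm, so at least 94 − 50 = 44 of 50 (88%) must come from the intervention arm. On this reading the rate is biased downward.

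**The case against.** The best case for the plan is this. Feasibility of the coaching already has its own measures: attendance out of 8 sessions, participants' ratings, and focus groups in the intervention arm. Heavy loss under coaching would probably show in attendance. Both arms receive a Fitbit and a prescription and follow the same assessment schedule, so overall retention is a legitimate quantity for planning a two-arm trial. The larger discordance figures rest on assumed gaps that the documents do not supply.

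Much of this stands. An overall rate is worth reporting, and the problem is small if coaching does not affect dropout. But attendance and retention differ: a participant can attend sessions and miss the final assessment, or stop the sessions and still be assessed, as Section 5.3.3 requests of those who withdraw. A difference in dropout between arms is also something a feasibility study should be able to show.

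A reader might infer four stronger things that the documents do not support:

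- *That the plan prescribes pooling.* It is silent. Nothing bars by-arm reporting; it is only not required.
- *That 75% is a pass mark.* It is stated as a prediction, with no progression rule attached.
- *That counting Phase 1 participants makes 75% easier to reach.* Step 4 shows the reverse, and in a sentence about the intervention Phase 2 is the more natural reading in any case.
- *That Aim 2 is compromised.* Withdrawn participants remain in the intent-to-treat analysis, and the maximum-likelihood model avoids list-wise deletion. Its validity does depend on why data are missing, which is a reason to report loss by arm, not evidence of bias.

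**Conclusion.** The point holds in two parts. The inverted numerator is a plain error and depends on no assumption. The missing arm, phase and completion visit are a gap in specification: with the numerator corrected, an overall 75% can coexist with 50% to 60% retention under coaching if the comparison arm retains 90% to 100%.

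How likely that is depends on assumed rates. For the gaps of 15 to 30 points examined, all with a two-arm average of 75% to 80%, the probability is 0.54 to 0.71 in four scenarios and 0.86 at 65%/95%. At equal rates of 75% to 80% it is 0.13 to 0.15. These figures assume 50 per arm, independent outcomes and a numerator of completers. They describe how far an overall rate could mislead; they do not forecast that it will.

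**What to change.** Replace the retention sentence in Section 7.9 with a definition that does the following:

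- Retention = participants completing the named assessment / participants randomised in Phase 2.
- Name that assessment, either post-intervention or 6-month follow-up, and say whether someone who stops coaching but attends it counts as retained.
- Report the rate by arm, with the between-arm difference and its 95% CI.
- Set the intervention-arm rate beside the predicted 75%, with the overall rate alongside.

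Loss between Phase 1 and randomisation can be reported separately.

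The change is to wording only and needs no new data. The cost is precision. At a rate of 75% the approximate 95% half-width is 1.96 × √(0.75 × 0.25 / 50) = 12 points for one arm, against 1.96 × √(0.75 × 0.25 / 100) = 8.5 points overall. For the difference, at 60% and 90%, it is 1.96 × √(0.6 × 0.4 / 50 + 0.9 × 0.1 / 50) = 16 points. The by-arm figures should therefore be read as estimates with their intervals.
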